### List of Abbreviations

[figure not shown]
*All abbreviations used throughout the protocol must be defined.*

AE	Adverse Event
CFR	Code of Federal Regulations
CRF	Case Report Form
CTSC	Clinical Translational Science Center
DSMB	Data Safety Monitoring Board
DSMP	Data Safety Monitoring Plan
FDA	Food and Drug Administration
GCP	Good Clinical Practice
HIPAA	Health Insurance Portability and Accountability Act of 1996
HRBFA	Human Research Billing Analysis Form
HUD	Humanitarian Use Device
ICF	Informed Consent Form
IDE	Investigational Device Exemption
IND	Investigational New Drug
IRB	Institutional Review Board
PHI	Protected Health Information
PI	Principal Investigator
REDCap	Research Electronic Data Capture
SAE	Serious Adverse Event
SUSAR	Suspected Unexpected Serious Adverse Reaction
UAP	Unanticipated Problem
WCM	Weill Cornell Medicine

### Protocol Summary

Full Title:	Post-operative Pain Control of Testicular Sperm Extraction Using Liposomal Bupivacaine
Short Title:	Liposomal Bupivacaine in sperm extraction
Clinical Phase:	IV
Principal Investigator:	[name]
Sample Size:	N= 85
Accrual Ceiling:	This study will enroll 85 subjects
Study Population:	Healthy men (>18yo) presenting for testicular sperm extraction for fertility
Accrual Period:	6 months
Study Design:	Double blinded randomized control trial comparing standard bupivacaine against standard bupivacaine plus liposomal bupivacaine. The local anesthetic will be injected into the surgical bed at the conclusion of the procedure prior to emergence from anesthesia. Each arm will have 25 men.
Study Duration:	Three weeks. Patients will keep a pain diary for 7 days post-op and will have a routine post-op clinic appointment at 3 weeks. Study projected end date: 7/2019.
Study Agent/	
Intervention Description:	Liposomal bupivacaine, 266mg/20mL. One dose (20mL) will be infiltrated into the wound at the end of surgery.
Primary Objective:	Area under the curve of pain rankings on the 11-point numerical pain rating scales (NRS-11) scale assessed every 8 hours in the first 48 hours post-surgery.
Secondary Objectives:	Area under the curve of pain rankings on the 11-point numerical pain rating scales (NRS-11) scale in the first 60 hours post-surgery. Area under the curve of pain rankings on the 11-point numerical pain rating scales (NRS-11) scale in the first 7 days post-surgery. Total number of narcotic tablets required between the intervention and control arms during post-operative day 1 through 7. Time to first rescue narcotic utilization between the two arms. Overall satisfaction of pain control regimen (self reported on post-operative day 7). The percentage of patients remaining opiate free by post-operative day 7.
Exploratory Objectives:	NA
Endpoints:	Study ends once 50 patients have undergone surgery and finished the surveys and post-surgical follow-up.

## 1. Study Objectives

### 1.1 Primary Objectives

Our primary endpoint is the area-under-the-curve in the first 48 hours post-surgery for 11-point numerical pain rating scales (NRS-11) of patients who were injected with liposomal bupivacaine (mixed with standard bupivacaine) at the time of surgery against standard bupivacaine only.

### 1.2 Secondary Objectives

Secondary endpoints:

Area-under-the-curve in the first 60 hours and 108 hours (7 days) post-surgery for 11-point numerical pain rating scales (NRS-11).

Average total number of narcotic tablets required between the intervention and control arms during post-operative day 1 through 7.

Time to first rescue narcotic utilization between the two arms.

Overall satisfaction of pain control regimen (ranked by the patients on post-operative day 7).

The percentage of patients remaining opiate free by post-operative day 7.

### 1.3 Exploratory Objectives

NA

## 2. Background

### 2.1 Disease

Approximately 640,000 men in the United States are azoospermic, a condition characterized by the lack of sperm in the ejaculate. For these individuals, microdissection testicular sperm extraction (microTESE or MESA) represents the only means to procure sperm for in vitro fertilization. Our center initially described the technique, which now represents the standard of care for these individuals [1]. Given the sensitivity of scrotal/testicular surgery, post-operative pain remains a major concern for our patient population.

1. Schlegel PN. Testicular sperm extraction: microdissection improves sperm yield with minimal tissue excision. *Human reproduction* (Oxford, England). 1999;14(1):131-135.

## 2.2 Investigational Agent or Device

Liposomal bupivacaine has garnered significant interest in the peri-operative arena. Multiple studies have now documented varying levels of success with intra-operative administration [1-3]. Relevant to our patient population, the liposomal delivery vehicle provides an extended release over 72 hours, which corresponds to the time-period of maximum narcotic utilization in men undergoing testicular sperm extraction. For this latter reason, we believe liposomal bupivacaine to be a promising adjunct to manage our patient population. As standard practice, we currently use 1/4% bupivacaine hydrochloride infiltrated into the peri-testicular tissue, the spermatic cord, and the scrotal wound. This agent only provides analgesia for ~6 hours.

The mechanism of action for both bupivacaine hydrochloride and liposomal bupivacaine is the same, intracellular binding of voltage gated sodium channels. This blockade prevents pain fibers from initiating and propagating an action potential. In the case of liposomal bupivacaine, the agent is packaged into liposomes in order to slow the release of the medication. This extends the theoretical period of action from 6 to ~72 hours. The Phase III trials that studied liposomal bupivacaine utilized a dose of 120mg [4] and 266mg [5]. These studies found liposomal bupivacaine effective against placebo for bunionectomy and hemorrhoidectomy [4-5]. Subsequently, a multitude of studies have used the 20mL vial (266mg), best described by a Cochrane Review/Meta-analysis [6]. These studies found a similar safety profile of liposomal bupivacaine compared to the standard preparation of bupivacaine. The pharmacokinetics were as follows:  $T_{1/2}$  23.8 – 34.1 hours,  $C_{max}$  166 – 867 ng/mL, and  $T_{max}$  0.5 – 2 hours [4-5,7]. Liposomal bupivacaine carries the same risks of CNS toxicity and cardiovascular toxicity as standard bupivacaine. Major drug interactions occur with simultaneous administration with lidocaine, which may destabilize the liposomes and cause premature release of the agent. We do not plan on use lidocaine due to this reason. Both standard and liposomal bupivacaine are metabolized in the liver and excreted primarily by the kidneys. We plan to exclude men with either hepatic or renal impairment.

### **2.3 Rationale**

In general, the management of post-operative pain remains a prominent goal of urologic practice. Given the rising incidence of opiate abuse, it is prudent to study non-opiate strategies to lessen the potential risk of long-term dependence [1-3]. Ambulatory surgery is an ideal candidate for optimization of pain management. Our group has previously reported success with the use of COX-2 inhibitors to diminish narcotic requirements [4]. In that study men undergoing testicular sperm extraction were randomized to celecoxib versus placebo. We demonstrated a significant decrease in the use of narcotics by post-operative day 2. Although encouraging, we strive to further improve our post-op pathway.

## **2.4 Risk/Benefit Assessment**

The risks to the patient include: reaction to the liposomal bupivacaine or standard bupivacaine (these are exceedingly rare, about 1 in 50,000 patients), inconvenience due to the pain diary, and the routine privacy concerns involving clinical studies. The benefits may include improved pain control with liposomal bupivacaine. Indirect benefits to society include an improved pain control regimen if the trial results are positive, or cost-savings should liposomal bupivacaine prove infective, therefore limiting potential overutilization of this expensive medication in the health care system. It is possible that the addition of liposomal bupivacaine will remove a significant amount of opiate requirement post-op, which may translate to reduced rates of eventual dependence/abuse. We believe the risk/benefit ratio is appropriate, as the reaction rates are similar between standard bupivacaine (already widely used) and liposomal bupivacaine, and there is reasonable expectation of equivalent or improved post-op pain control given that both arms receive current standard of care (i.e. at least 20mL of 0.25% standard bupivacaine). Privacy concerns will be handled in typical fashion in line with WCMC policies (coded data, secure storage, de-identification, etc.).

## **3. Subject Selection**

### **3.1 Study Population**

Healthy patients presenting with a diagnosis of infertility, in which surgical sperm extraction is planned, will be offered inclusion into the study.

### **3.2 Inclusion Criteria**

- 1) Men scheduled for MicroTESE sperm retrieval for infertility
- 2) Men 18 years and older who can provide informed consent
- 3) No documented allergy to bupivacaine or celecoxib

### **3.3 Exclusion Criteria**

- 1) Prior history of substance abuse (narcotics, alcoholism)
- 2) Any narcotic use within the last 3 months
- 3) Concomitant use of aspirin
- 4) Any of the following comorbidities: renal failure, heart disease, peptic ulcer

disease, cerebrovascular disease, significant liver disease, untreated depression, chronic pain disorder, or bleeding diatheses

5) Medical history or concurrent illness that the investigator considers sufficiently serious to interfere with the conduct, completion, or results of this trial, or constitutes an unacceptable risk to the subject

#### **4. Registration Procedures**

##### **4.1 Patient Registration**

Patients will be centrally registered with the Office of Billing Compliance. To register a patient, we will submit the following documents via the JIRA Registration Process:

- Legible copy of the HRBAF
- First and last page of signed informed consent form

Registration will be completed within 24 hours of the signing of informed consent.

#### **5. Study Procedures**

##### **Visit one: Pre-op clinic appointment**

The patients will be seen within 1 month of their scheduled sperm extraction per our usual practice patterns. At this time, they will be offered inclusion into the study if they meet criteria. Informed consent will take place at this time.

##### **Visit two: Day of sperm extraction**

The patients will present to the ambulatory surgical center. On the day of the procedure, randomization will take place (1:1 ratio, standard bupivacaine versus standard bupivacaine plus liposomal bupivacaine). A computer-generated randomization scheme will be used. The attending surgeon will not know the randomization outcome until the conclusion of the surgery, the point at which local anesthetic is administered prior to final wound closure. He will be scrubbed out by an unblinded surgeon, who is not otherwise involved in subsequent patient contact, for administration of the local anesthetic. Note that this is necessary since liposomal bupivacaine has a different appearance than standard bupivacaine. The appropriate local anesthetic will be administered, the wound closed, and the patient awoken from anesthesia. The patient will remain blinded to which local anesthetic was used for the entire study.

##### **Post-operative recovery: week 1**

Study participants will complete online surveys generated from RedCap x 7 days. The survey will be administered every 8 hours in days 1-2, and every 12 hours in days 3-7. The surveys will ask the patients to rank their current pain (NRS-11), pain control satisfaction, and record the number of narcotic tablets required.

During the standard of care post-op call, the nurse will ask and record complications and also address patient questions.

Post-op visit (2-3 weeks post-op):

The post-op clinic visit allows for a routine wound check and a discussion of results. The subject will have an opportunity to ask questions regarding the surgery, should any debriefing be required.

### 5.1 Schedule of Evaluations

**Table 1. Schedule of trial events**

	Pre-op clinic visit	Day of procedure	First week post-op	Post-op visit
Agent Administration		X		
Informed consent	X			
Demographics	X			
Medical history	X			
Physical exam	X	X		X
Vital signs	X	X		X
Adverse event evaluation		X	X	X
Outcome evaluation (online survey)		X	X	X

For a day-by-day description, please refer to the prior section.

### 5.2 Treatment Administration

The attending surgeon will not know the randomization outcome since he will be replaced by a second, unblinded surgeon for the portion of the case requiring administration of the local anesthetic. This is necessary since liposomal bupivacaine has a different appearance than standard bupivacaine. The control arm will receive 40 mL of 0.25% standard bupivacaine. The intervention arm will be given 20 mL of 0.25% standard bupivacaine mixed with 20mL/266mg of liposomal bupivacaine. The 20 mL of 0.25% standard bupivacaine given to the intervention arm will insure an adequate block initially (liposomal bupivacaine has a delayed effect). Note that the mixing of 20mL/266mg of liposomal bupivacaine with 20mL of 0.25% standard bupivacaine has been evaluated in phase IV trials, and is now recommended practice as reflected in the FDA drug insert [1]. The appropriate local anesthetic

mixture is administered, the wound closed, and the patient awoken from anesthesia. No other local anesthetics will be available on the surgical field, as these are the most likely agents to adversely react with liposomal bupivacaine (i.e. lidocaine).

1. Mont MA, et al. Local Infiltration Analgesia With Liposomal Bupivacaine Improves Pain Scores and Reduces Opioid Use After Total Knee Arthroplasty: Results of a Randomized Controlled Trial. *The Journal of arthroplasty*. 2018;33(1):90-96.

### **5.3 General Concomitant Medication and Supportive Care Guidelines**

None

### **5.4 Duration of Therapy and Criteria for Removal from Study**

- Not applicable – the study medication is administered once prior to wound closure during the surgery. Subjects may voluntarily withdrawal from the survey-portion of the study at anytime without consequences to their subsequent care.

### **5.5 Duration of Follow Up**

Patient are routinely called on post-operative day one to ensure a smooth recovery and answer any practical questions (dressings, wound care, etc.). Any unexpected outcomes will be recorded by the study nurse. Should a serious event occur, the patient will be forwarded to the emergency room for further evaluation.

## **6. Dosing Delays/Dose Modifications**

Dose modification is not anticipated. Should a patient be allergic to local anesthetics, or pre-operative medical conditions that may serve as a contraindication to bupivacaine, they will be identified and excluded during the pre-operative visit.

## **7. Pharmaceutical Information**

### **7.1 Investigational Agent**

Liposomal bupivacaine is pre-packaged in sterile, 20mL/266mg vials that are single-patient use. No reconstitution or special handling required. The medication is stable at

room temperature and can be stored as such for more than a year (personal discussion with the manufacturer).

The risks of liposomal bupivacaine are similar to standard bupivacaine, which include:

Allergic reaction

If administered at toxic dose (occurs 1 in 50,000 patients per the FDA):

All local anesthetics have similar cardiovascular and nervous system effects:

- Cardiovascular – depression, arrhythmia, and heart block
- Nervous system – excitation or depression (varies), which can lead to respiratory depression

Note that the phase III trials have established 20ml/266mg as the standard dose.

The mixing of 20mL/266mg of liposomal bupivacaine with 20mL of 0.25% standard bupivacaine has been evaluated in phase IV trials, and is now recommended by the manufacturer and is reflected in the FDA drug insert [1]. Finally, unique to liposomal bupivacaine, concomitant administration with lidocaine can destabilize the liposomal vehicle. To remove this risk, lidocaine will not be allowed to be in the operating room during the case.

1. Mont MA, et al. Local Infiltration Analgesia With Liposomal Bupivacaine Improves Pain Scores and Reduces Opioid Use After Total Knee Arthroplasty: Results of a Randomized Controlled Trial. *The Journal of arthroplasty*. 2018;33(1):90-96.

## **7.2 Availability**

Liposomal bupivacaine is available from the manufacturer or a multitude of third party wholesalers.

## **7.3 Agent Ordering**

The required amount of medication to complete the study (25 vials), will be ordered from a third party wholesaler.

## **7.4 Agent Accountability**

Liposomal Bupivacaine Inventory Records – The investigator, or a responsible party designated by the investigator, will maintain a careful record of the inventory and disposition of all agents on a Drug Accountability Record Form (DARF).

## **8. Correlative/Special Studies**

Not applicable – no correlative or special studies

## 9. Measurement of Effect

### 9.1 Response Criteria

The patients will be prompted to complete online surveys administered through REDCap. REDCap allows for HIPAA compliant data gathering through this format. Surveys will include the following: a numerical rating scale (0 through 11) to rank current pain, number of narcotic tablets consumed since the prior survey, and overall satisfaction of pain control (binary yes/no).

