### **11.4 Analysis of Endpoints**

#### **11.4.1 Analysis of Primary Endpoints**

Area-under-the-curve of the NRS-11 in days 1 and 2 ( $AUC_{days1-2}$ ) will be compared in treatment vs control groups using a two-sample t-test allowing for unequal variances, with a two-sided alpha of 0.05. A 95% confidence interval for the difference in  $AUC_{days1-2}$  between arms will be estimated along with estimate and confidence intervals of average  $AUC_{days1-2}$  within each arm. If significant deviations from normality are observed in  $AUC_{days1-2}$ , a non-parametric Mann-Whitney test will be used instead.

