#### **11.4.2 Analysis of Secondary Endpoints**

$AUC_{60\_hrs}$  will be similarly analyzed as the primary endpoint.

$AUC_{days1-7}$  will be similarly analyzed as the primary endpoint.

Total number of narcotics tablets required will be analyzed with a Poisson regression, with a relative rate estimated with appropriate 95% confidence intervals.

Time to rescue narcotic requirements will be assessed with Kaplan-Meier and cumulative incidence curves. A log rank test will be used to compare treatment and control arms. If no censoring occurs, mean time to rescue narcotics will be assessed with a t test and 95% confidence intervals obtained.

The percentage of patients who remain opiate free and the percentage of patients who are overall satisfied with pain control on day 7 will be analyzed with a chi-squared test, and a 95% confidence interval for the difference in proportions estimated.

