### 13. Data and Safety Monitoring Plan (DSMP)

In this section, please include a written plan of the measures that will be taken to ensure the safety of clinical research subjects and protect the validity and integrity of research data. The following questions should be addressed as a part of the DSMP and must be incorporated into your WCM eIRB application:

- Adverse events will be recorded by the study nurse and clinical fellow during follow-up phone calls and clinic visits with each post-operative patient. Minor adverse events will be examined and reviewed for intervals of every 10 patients during accrual. Any significant adverse events (allergic reaction, central nervous system or cardiotoxicity) will trigger a temporary cessation of the trial and full review by the principal investigator.
  - Study stopping rules/protocol: the only stopping rule is if an SAE occurs, the study will be stopped fully. A full review by the PI will then take place and the IRB, FDA, and Pacira Pharmaceuticals, Inc. will be queried as to when and if the study should continue.
- Data
  - Adverse event data
    - Major: Allergic reaction, central nervous system and cardiotoxicity
    - Minor: poor pain control, extended hospital stay, wound infection, scrotal hematoma, wound dehiscence, urinary retention, nausea, vomiting, diarrhea
  - Study-related data
    - Pain scores (NRS-11), Narcotic tablet tally, overall pain control satisfaction (Yes/No question)
  - Demographics
  - Patient age, male infertility diagnoses (i.e. presence of varicocele), prior surgical history, current medications, historical lab evaluation (FSH, LH, total testosterone, semen analyses, sperm DNA integrity tests such as tunel or SCSA assay, karyotype data, y-microdeletion status), pathology results of testis biopsy
- Data safety
  - Data will be kept in REDCap, which is licensed by WCMC and is HIPAA compliant. Only study personnel will have access to the database. Hard or software copies of the database will not be allowed. The database will only be accessed within the WCMC network utilizing WCMC tagged devices. Patient identifiers will be replaced by study identifiers as soon as data collection is complete.

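### Satisfaction is called ranked in 1.2 but captured and analysed as yes/no; the plan can be run, but a graded item would keep information at little cost

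*Combined protocol and SAP*

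**What the plan says.** All references are to the combined protocol and SAP.

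- 1.2 Secondary Objectives: "Overall satisfaction of pain control regimen (ranked by the patients on post-operative day 7".
- 5 Study Procedures, first post-operative week: the surveys ask patients to "rank their current pain (NRS-11), pain control satisfaction, and record the number of narcotic tablets required". A scale is named for pain only.
- 9.1 Response Criteria: the survey includes "overall satisfaction of pain control (binary yes/no".
- 13 Data and Safety Monitoring Plan: the study data include "overall pain control satisfaction (Yes/No question".
- 11.4.2 Analysis of Secondary Endpoints: "the percentage of patients who are overall satisfied with pain control on day 7 will be analyzed with a chi-squared test", with a 95% confidence interval for the difference in proportions.
- Protocol Summary: "Overall satisfaction of pain control regimen (self reported on post-operative day 7", which fits either kind of item.

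No section gives levels or anchors for a satisfaction scale, or an ordinal test. No section gives an expected satisfaction rate, a target difference or a power for this endpoint.

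**The concern.** The objective, read literally, calls for a graded answer, but the item in 9.1 and 13 can record only two values. The documents need one definition of the endpoint.

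The choice also affects what the trial can learn. A yes/no item splits an underlying degree of satisfaction at one point. If most men in both arms fall on the same side of that point, few answers separate the arms. With 25 per arm, a finding of no difference could then mean equal satisfaction or simply too few men answering no. The loss cannot be repaired later: a rating can be dichotomised after the fact, but a yes/no answer cannot be graded.

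**Working it through.** **Inputs from the document.** 25 patients per arm, 1:1 allocation, 2.4-point difference, SD 2.75 and 85% power, all for the pain AUC (11.2). The test level, "with a two-sided alpha of 0.05", is stated for the primary endpoint (11.4.1) and is assumed here for satisfaction.

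**Assumptions, because the document is silent.** Satisfaction has a normal latent score that shifts by *d* SD under treatment. A control man says yes with probability p_C, taken as 70%, 80% or 90%. The main case is *d* = 0.8; *d* = 0.5 and *d* = 0.873 are also shown.

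**Step 1: the plan's own figure.** 2.4 / 2.75 = 0.873 SD. Two-sample t-test power with 25 per arm is 0.856, so the stated 85% reproduces. It is the power for pain AUC, not for satisfaction. It shows that *d* = 0.8 is close to the effect size the trial was planned on.

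**Step 2: yes/no power.** The treated yes-rate is p_T = Φ(Φ⁻¹(p_C) + *d*). For p_C = 80% and *d* = 0.8: Φ(0.842 + 0.8) = Φ(1.642) = 95.0%. With *a* and *b* men saying yes and p̄ = (*a* + *b*)/50, the uncorrected chi-squared test rejects when |*a* − *b*|/25 divided by √(2p̄(1 − p̄)/25) exceeds 1.96. Power is the sum of the two binomial probabilities over every rejecting pair (*a*, *b*).

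**Step 3: rating power.** Same latent score, cut into 11 levels equally likely in controls, Mann-Whitney test, simulated: about 76% at *d* = 0.8. If 60% of controls give the top score, about 56% (55% to 57% across runs).

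**Step 4: loss = 1 − (yes/no power ÷ rating power), at *d* = 0.8.**

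| Control yes-rate | Treated yes-rate | Yes/no power | Loss against 76% | Loss against 56% (ceiling) |
|---|---|---|---|---|
| 70% | 90.7% | 48% | 1 − 48/76 = 37% | 1 − 48/56 = 14% |
| 80% | 95.0% | 38% | 1 − 38/76 = 50% | 1 − 38/56 = 32% |
| 90% | 98.1% | 16% | 1 − 16/76 = 79% | 1 − 16/56 = 71% |

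**Step 5: sensitivity to *d*.**

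- *d* = 0.873: yes/no 54%, 42% and 17% at the three rates; 11-level rating about 82%, or about 61% with the ceiling.
- *d* = 0.5: yes/no 25%, 21% and 11%; rating about 38%, or 27% to 28% with the ceiling. Neither is well powered.

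**Step 6: upper limit of the yes/no item.** Even if every treated man says yes, power is 77% at a control rate of 80%, 53% at 85% and 24% at 90%.

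**The case against.** The strongest reply is that the operational plan is coherent. Measurement (9.1), data list (13) and analysis (11.4.2) all agree on a binary item, and a statistician could run the analysis as written. The only text against it is one word in 1.2 and a loosely built sentence in 5. Section 9.1 itself uses *rank* for pain and, in the same sentence, makes satisfaction binary. A satisfied-or-not question is a legitimate choice, the trial was sized only for pain AUC, and the planned confidence interval would show the imprecision. The survey attachment mentioned in 10.1, which would show the actual item, is not among the documents.

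Most of this stands. Three stronger readings that a reader might infer are not supported:

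- **That a graded rating was planned and then lost.** No satisfaction scale is defined anywhere. The 0-10 rating is proposed here, not recovered from the plan.
- **That yes/no removes most of the power whenever most men are satisfied.** At 70% yes the loss is 37%, and at 80% it is half. It is clearly more than half only from about 85%, and the documents give no rate.
- **That a power statement is wrong.** None was made for satisfaction.

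What the reply does not remove is the wording conflict, or the fact that the graded item did better in every case compared here, ceiling included.

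**Conclusion.** The point holds as a wording conflict plus a cheap design improvement, and it is minor. Sections 1.2 and 5 do not match 9.1, 11.4.2 and 13, and they should be reconciled whichever item is used.

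The power cost of yes/no is conditional. At an assumed shift of 0.8 SD it is between about one third and just under four fifths of the rating's power as the control yes-rate goes from 70% to 90%. With a heavy ceiling on the rating, it is 14% to 71%. At 0.5 SD both items are weak, so a rating would not rescue a modest effect.

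These figures rest on a normal latent score, a uniform shift, 25 men per arm with a day-7 answer, and yes-rates that the documents neither give nor imply. They show direction and rough size; they do not predict this trial's power.

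**What to change.** **Preferred.** Add a 0-10 satisfaction rating with stated anchors to the day-7 REDCap survey. Surveys run every 12 hours on that day, so name the one that counts. In 11.4.2, compare arms by Mann-Whitney with a Hodges-Lehmann difference and 95% confidence interval. Keep the yes/no percentage by arm as a descriptive summary. Align 1.2, 5, 9.1, 11.4.2 and 13.

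**Cost.** One survey field, revised wording and an IRB update. Patients already give a numerical pain rating in the same survey, so the added burden is small. The main result becomes slightly less simple to quote, which the retained percentage offsets. The change has to precede data collection.

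**If the sponsor keeps yes/no.** Replace *ranked* in 1.2, reword the sentence in 5 so that *rank* applies to pain only, and state that the comparison is imprecise and that a null result is not evidence of equal satisfaction. Consider an exact test too: at 80% against 95% yes, the expected number of no answers is 25 × (0.20 + 0.05)/2 = 3.1 per arm, which is low for chi-squared.
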